**5.53d Subsequent Enrollment in a Therapeutic Drug Trial**

Participants in this study may enroll in a therapeutic drug trial at any point after signing consent to participate in this study. However, if a patient enrolls in a therapeutic drug trial that requires structured symptom or toxicity reporting we will record this and perform a sensitivity analysis, excluding any patients who participated in a therapeutic trial after enrollment, to determine whether this impacts our findings. Since this is a feasibility and acceptability trial, we do not want to censor participants.

**5.54 Compensation**

In the first phase, there will be no compensation for participants in this study. However, participants will be allowed to keep the wearable accelerometers (approximately \$200 value) and will be provided with phone chargers to compensate for battery drainage that may be caused by installing the HOPE App (approximately \$15 value). In the second phase, participants who are randomized to the corresponding arms will be allowed to keep the wearable accelerometer and/or receive a phone charger if requested. All

patients will be provided with a gift-card after the 1-month, 3-month, 6-month interviews to minimize attrition and prevent differential drop-out by study arm. The incentives will be \$20 at 1 month, \$30 at 3 months, and \$50 at 6 months. Subjects who are randomized to arm 4 (passive app) will also receive a \$20 gift card after the first study interview at baseline.

In addition, if subjects incur additional costs related to their phones' data plan use as a result of participating in the study, subjects will be asked to provide the study team with receipts, and study-related expenses will be reimbursed. Subjects will be provided with an information sheet (Appendix AA: Patient Reimbursement Info Sheet) describing the reimbursement process.

## 5.6 Adverse Reactions and Their Management

### 5.6.1 Reporting Adverse or Unanticipated Events

Potential adverse events (AE) for this project are expected to be all non-medical in nature. There is small risk of physical injury. Participants could experience discomfort while wearing the Fitbit Charge 2 on their wrist. There is also a chance participants could worsen repetitive use injuries (e.g., carpal tunnel syndrome) while using the smartphone app. Subjects may experience mild anxiety when answering survey questions about emotional issues or questions about coping challenges or difficulties related to discussing the subject matter. The PI will report unanticipated and serious adverse events to the IRB in a timely manner on an ongoing basis. For the purpose of this study a Serious Adverse Event (SAE) is defined as an event that, as a direct result of the study, causes serious harm to the subject (e.g., hospitalization).

### 5.6.2 Anticipated Reactions & Reaction Management

Should participants become exceedingly upset, disoriented or fatigued or need to attend to matters of personal care during the surveys, study staff will ask the subject if they would like to take a break or reschedule the survey for another time. In the event that participants experience distress while completing surveys, we will follow standard procedures used in our behavioral health intervention studies for counseling and referral. The PI will be notified immediately, and participants will be provided with the pager numbers for both the study PI and the study psychiatrist included in the consent form. [name], a DFCI psychiatrist, has agreed to serve as a psychiatrist on the study. [name] will evaluate any participants who are distressed for risk of imminent danger and refer them to appropriate services if they are needed.

As noted in the study procedures, all clinical staff will be trained in the study protocol. A participants' clinical care team will be notified of every incoming call to the triage nurses, per standard practice, and her physician will be paged in the case of an emergency.

## 6.0 STATISTICAL ANALYSIS

### 6.1 Primary and Secondary Endpoints

#### Primary Endpoints: First Phase

- 1) To assess the feasibility and acceptability of the HOPE app and the two wearable accelerometers
- 2) To compare two wearable accelerometers (Fitbit Zip and Fitbit Charge 2) with respect to correlations with clinical outcomes (ECOG PS and patient-reported quality of life and physical health as measured by the PROMIS Global-10 items 2 and 3), for use in pilot RCT.

#### Secondary Endpoints: First Phase

- 1) To describe correlations between data collected from the HOPE app and the wearable accelerometers with additional clinical outcomes: PRO-CTCAE, CTCAE, and EQ-5D-5L.

#### Primary Endpoint: Second Phase

- 1) Health-related quality of life, comparing the patient-reported baseline and 6-month EuroQol EQ-5D.

#### Secondary Outcomes: Second Phase

- 1) Health care utilization (i.e. emergency room visits, hospitalizations, unplanned infusion appointments, and number of patient phone calls)
- 2) Correlation between patient and physician estimates of performance status
- 3) Additional clinical outcomes (e.g. anxiety and depression).
- 4) Correlation between data collected from the wearable and smartphone accelerometers
- 5) Predictive ability of wearable and smartphone accelerometers for patient's performance status and clinically significant events
- 6) Difference in correlation between data collected from the wearable and smartphone accelerometers, and difference in predictive ability of smartphone accelerometers for patient's performance status and clinically significant events, by whether patients are encouraged to wear their smartphones

### 6.2 Sample Size and Statistical Power or Precisions

A convenience sample of 10 patients will be enrolled to the first phase of the study. Due to the limited sample size, statistical analysis will be descriptive in nature.

100 patients will be enrolled to the second phase of this study, which will employ a 2x2 factorial design as depicted in the table below. Patients will be randomized 1:1:1:1 to one of the four arms.

Fitbit	App	Arm	Sample size
+	Active	1 (Fitbit + active app)	25
+	Passive	2 (Fitbit + passive app)	25
-	Active	3 (Active app)	25
-	Passive	4 (Passive app)	25
		Total	100

For the outcome of change in EQ-5D, we will use a one-sided type I error rate of 5% to conclude that an intervention is promising for further study. Based on prior literature, the standard deviation of the change in EQ-5D at 6 months compared to baseline is approximately 14 points. With a total sample size of 100 patients (25 patients per arm), the table below summarizes the power to conclude that the either or both of the interventions are promising for further study based on a variety of effect sizes.

Difference in EQ-5D versus Usual Care			Power to conclude that intervention is promising for further study	
HOPE App	Wearable accelerometer	HOPE App + Wearable accelerometer	HOPE App	Wearable accelerometer
6	0	6	70%	--
7	0	7	80%	--
6	3	9	70%	28%
7	3	10	80%	28%
6	3	8	62%	23%
7	3	8	68%	17%

### 6.3 Intervention Allocation Plan

In the second phase, enrolled participants will be randomized to one of the four arms: 1) Fitbit + active app, 2) Fitbit + passive app, 3) Active app, 4) Passive app—using a 1:1:1:1 ratio. Enrolled participants will undergo a secondary randomization to being encouraged to use a smartphone, or not encouraged to use a smartphone. Randomization to the main study arms will occur using a computer-generated random allocation sequence with blocks of 8 in order to maintain balance between study arms over time. Study staff will generate group assignments in sequentially numbered and sealed opaque envelopes.

## 6.4 Analysis Plan

### First phase:

Due to the limited sample size, statistical analysis will be descriptive in nature. Refinement of the HOPE App and selection of the wearable accelerometer to use in the second phase will be based on a descriptive assessment of feasibility, acceptability, and correlations with clinical outcomes.

Feasibility: We will record the proportion of eligible patients who enroll in the study and basic reasons for refusal [i.e. “too busy,” “not interested,” “other (specify)’]. Among those who enroll, we will plot the proportion who complete daily (quality of life, self-rated health, and PRO-CTCAE questions) and weekly (Promis PF 6b) surveys from the HOPE App over time, and the average steps per day obtained from each of the accelerometers. We will also descriptively summarize the proportion of clinicians complete the CTCAE and performance status data for enrolled patients at baseline and post-baseline.

Acceptability: Upon completion of the study, participants will be asked several questions, including: 1) “Participating in this study placed a substantial burden on me” and 2) “I wish I had not agreed to participate in this study.” Responses to these items will be summarized descriptively.

#### Refinement of the HOPE App:

Participants will be asked about their experiences using the HOPE app, including: “Was the app helpful for managing your symptoms?” Participants will be asked about the frequency, format, and content of the app-based surveys, and whether there were symptoms that were missing from the app. Participants will also be asked open-ended questions, including: “What did you like about the app?” “What was most frustrating [about the HOPE app]?", “How could it [the HOPE app] have better met your needs?”, and “Would you recommend this to a friend going through treatment? Why?” Responses to these items will be summarized descriptively.

#### Comparison between two wearable accelerometers:

Participants will also be asked several questions about their experience using the Fitbit, including: “Which Fitbit did you like better?” Response options will include: “Fitbit Zip (worn on your waistband),” Fitbit Charge 2 (worn on your wrist),” “No preference,” and “Neither.” Participants will be asked an open-ended question: “Why did you like the [FitbitZip/Fitbit Charge 2] better?” Participants will also be asked to what extent they agree with the following questions: “The Fitbit Charge 2 was easy to use” and “The Fitbit Zip was easy to use.” We will also ask participants how many waking hours they wore each device daily (i.e. % waking hours), and how many times they forgot to wear the device or forgot to recharge it. Responses to these items will be summarized descriptively.

#### Correlations with clinical outcomes:

We will descriptively summarize correlations between data collected from the HOPE app (quality of life and physical function) and the wearable accelerometers (average daily steps) with clinical outcomes collected at baseline and post-baseline (i.e. performance status, quality of life, and symptoms assessment as obtained from the PRO-CTCAE and CTCAE).

**Second phase:**

In addition to descriptive analyses and estimating correlations between passive smartphone data and clinical outcomes, passive data may contain information that allows for the prediction of future clinically-relevant events, such as visits to the emergency department, urgent clinic encounter, or hospitalization. By testing for changes in activity, mobility, and social patterns over time as measured through smartphone use may be able to identify significant anomalies in patient behavior in the days prior to relapse. In a study in a cohort with schizophrenia, behavioral anomalies detected in the two weeks prior to clinical relapse occurred at a rate 71% higher than anomalies detected on other days. The method is based on a modification of the Hotelling's T test to detect changes in the distribution of previous passively-measured activity. In our proposed study, this method might be used to query patients in real time to detect if an unscheduled clinical event might occur in the near future. Analyses will be repeated within secondary randomization arm to explore whether correlations and predictive ability of information from smartphone accelerometers are lower when participants are not encouraged to wear their smartphones.

For the primary analysis, the EQ-5D index scores will be calculated in each study arm at both baseline and 6 months and compared. The effect of the Fitbit on EQ-5D will be obtained by comparing the mean change in EQ-5D among all arms that consist of the Fitbit (i.e. arms 1 and 2) versus that obtained among all arms that do not consist of the Fitbit (i.e. arms 3 and 4). Similarly, the effect of the HOPE app on EQ-5D will be obtained by comparing the mean change in EQ-5D among all arms that consist of the HOPE app (i.e. arms 1 and 3) versus that obtained among all arms that do not consist of the HOPE app (i.e. arms 2 and 4). Additionally, pair-wise comparisons will be conducted of arms 2, 3, and 4 to arm 1 to examine which arms are driving or diluting any differences observed. Mean score changes from baseline will be compared using t tests and multivariable linear regression. The multivariable linear regression model will consist of change score as the dependent variable, and will adjust for baseline covariates (age, sex, cancer type, race, education, and literacy and numeracy). Additional analyses will use Fisher's exact test to compare the proportion of patients in each study arm who experience an improvement, no change, or a decrement in quality of life. This will be conducted both for any level of change from baseline and for a 6-point change from baseline (the threshold for a clinically meaningful difference). Similar analyses will be conducted for the secondary outcomes, including anxiety, depression, and number of patient phone calls, using the appropriate regression model (e.g. negative binomial regression may be used for the outcome of the number of patient phone calls).

For the health care utilization endpoints of unplanned infusion appointments, emergency room visits, and hospitalizations, cumulative incidence functions will be calculated with death treated as a competing event. Competing risk regressions will be used to model risk with and without adjustment for baseline covariates.

Agreement between patient-oncologist estimates of performance status will be estimated by Cohen's Kappa statistic, and differences in agreement between the study groups will be tested by bootstrapping.

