- Hypothesis: Data collected from the wearable accelerometers and smartphone accelerometers (via passive app) will be significantly correlated with each other, and will provide quantitative measures that are correlated with patients' performance status and will be predictive of clinically significant events (hospitalizations, emergency department visits, and chemotherapy appointments)
- Hypothesis: The correlation between the wearable accelerometers and smartphone accelerometers (via passive app) will be higher in patients randomized to be encouraged to wear their smartphone at all times, and the predictive ability of the smartphone accelerometers for patients' performance status and

clinically significant events will be greater in in patients randomized to be encouraged to wear their smartphone at all times.

- Hypothesis: Participants will express more negative affect and anxiety related to their cancer experience in the weeks preceding scans, compared with the weeks when scans are not performed. This association will be moderated by participants' coping style (as measured by the brief COPE).

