### **5.34 Encouragement to Wear Smartphone**

In Phase II of the study, participants will be randomized both to a main study arm and a secondary randomization. The secondary randomization will randomize patients either to be encouraged to wear the smartphone at all times during the study (n=50), or not encouraged to wear the smartphone at all times during the study (n=50). Participants who are randomized to the “encouraged” arm will receive an appliance (e.g belt clip/arm band) which will allow them to carry their smartphone with them throughout the day, including while they would not ordinarily carry their smartphones with them (such as when walking around inside the home.) Participants who are randomized to the “not encouraged” arm will not receive any instructions about keeping their smartphone with them, and will not be provided with an appliance to carry their phone throughout the day.

**Figure 3.** Symptom classification and response in the *active* smartphone app intervention

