#### **5.52b Wearable Accelerometers:**

All participants will also receive a Fitbit Zip and Fitbit Charge 2. Participants in the Fitbit and Fitbit+HOPE App arms of Phase II of the study will receive only the Fitbit Charge 2.

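### Secondary outcome 6 is a randomised difference between encouragement groups, but the plan specifies no estimate of that difference with a confidence interval and no test

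*Combined protocol and SAP*

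**What the plan says.** All references are to Part 1, the HOPE Trial.

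- **The randomisation.** Section 5.34 allocates patients to be "encouraged to wear the smartphone at all times during the study (n=50), or not encouraged" (the other 50). Section 5.12 expects encouragement to have no effect on quality of life, performance status or health care use. That leaves the phone-data question as its purpose.
- **The hypothesis.** Section 2.2 predicts that the wearable-phone correlation "will be higher in patients randomized to be encouraged to wear their smartphone at all times", and makes the same directional claim for the phone's predictive ability.
- **The endpoint.** Section 6.1, Secondary Outcomes: Second Phase, item 6, is worded as a contrast by encouragement: "Difference in correlation between data collected from the wearable and smartphone accelerometers, and difference in predictive ability of smartphone accelerometers".
- **The analysis.** One sentence in Section 6.4, Second phase, covers it: "Analyses will be repeated within secondary randomization arm to explore" whether the correlations and the phone's predictive ability are lower in patients who are not encouraged.
- **Who has a wearable.** Section 5.52b: "Participants in the Fitbit and Fitbit+HOPE App arms of Phase II of the study will receive only the Fitbit Charge 2". These are arms 1 and 2.
- **How allocation is balanced.** Section 6.3: "Randomization to the main study arms will occur using a computer-generated random allocation sequence with blocks of 8". No method is given for the secondary randomisation.

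**The concern.** The endpoint is a difference between two randomised groups. The stated method gives one set of results in each group and stops. Nothing says how the two are to be set against each other or how uncertain their difference is.

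Without a stated contrast, the natural ways to read two separate results are to see which is significant or whether their intervals overlap. Both are unreliable with about 25 patients per group. The first can suggest an effect that is not there, and the second can hide one that is. A full randomisation and a supply of carrying appliances were added for this question, so its main result should be stated with its uncertainty. If the measure is left open until the data are seen, it can also be chosen after the fact.

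**Working it through.** **1. Is a contrast given anywhere else?** Section 6.2 sizes only the EQ-5D comparisons. In Section 6.4, the sentence extending the EQ-5D methods to other secondary outcomes follows the four-arm comparisons and names anxiety, depression and phone calls. Those methods compare outcome levels, not correlations. The bootstrap in the same section is for differences in Kappa agreement on performance status. None of these covers item 6.

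**2. The plan's own power figures.** Inputs from Section 6.2: SD 14, one-sided 5%, 50 v 50. SE = 14 × √(2/50) = 2.80; power = Φ(difference/2.80 − 1.645).

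- 6 points: 69.1% (stated 70%)
- 7 points: 80.4% (stated 80%)
- 3 points: 28.3% (stated 28%)

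These reproduce, but concern EQ-5D only. No power or precision is stated for encouragement.

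**3. Patients available.** The wearable-phone correlation needs a Fitbit: 25 + 25 = 50 patients, so about 25 v 25 by encouragement. That split is an assumption, because only the main-arm blocking is described. Predictive ability of phone data can use all arms, 50 v 50.

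**4. Reading two separate significance results.** Take one pair of summary values per patient, 25 per group and the same true correlation r in both. The chance that one group is significant at two-sided 5% is p = Φ(atanh(r) × √22 − 1.96). The chance that exactly one is significant is 2p(1 − p).

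| r in both groups | p | exactly one significant |
|---|---|---|
| 0.3 | 0.306 | 42% |
| 0.4 | 0.511 | 50% |
| 0.5 | 0.731 | 39% |

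**5. Reading overlap of intervals.** Suppose the observed correlations are 0.8 and 0.5, with 25 patients each. The 95% intervals, tanh(atanh(r) ± 1.96/√22), are 0.59 to 0.91 and 0.13 to 0.75, which overlap. The direct contrast is:

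- z difference = 1.099 − 0.549 = 0.549
- SE = √(1/22 + 1/22) = 0.302
- ratio = 1.82, one-sided p about 0.03

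Combining the two intervals gives an approximate 95% interval for the difference of 0.30:

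- lower limit: 0.30 − √((0.80 − 0.59)² + (0.75 − 0.50)²), about −0.02
- upper limit: 0.30 + √((0.91 − 0.80)² + (0.50 − 0.13)²), about 0.68

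Overlap alone conveys none of this.

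**6. What a direct contrast could show (illustration only).** Power = Φ(z difference/0.302 − 1.645), one-sided 5%. The documents give no correlations and no alpha for this comparison.

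| Not encouraged v encouraged | z difference | Power |
|---|---|---|
| 0.5 v 0.7 | 0.318 | 28% |
| 0.6 v 0.8 | 0.405 | 38% |
| 0.5 v 0.8 | 0.549 | 57% |
| 0.3 v 0.8 | 0.789 | 83% |

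Starting from 0.5, 80% power needs about 0.86 in the encouraged group.

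**The case against.** A reader might infer that the plan never compares the groups, or cannot answer its question. The text does not support that. Section 6.4 states a comparative purpose, and the same analysis run in two randomised groups yields two estimates whose difference follows by subtraction. Nor does any section say that the results will be judged by eye. What is absent is a defined estimate of the difference with its uncertainty.

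The analysis is also declared exploratory. It serves the last of six secondary outcomes in a pilot, and no decision depends on it. That stands: a formal test is not essential. It does not remove the need for an interval, because the endpoint itself is a difference, and low power makes the interval more useful.

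The power figures are open to challenge too. They assume one independent pair per patient. Fitbit data are minute by minute and, by Table 3, run to day 180, and the plan does not say whether the correlation is across patient averages or within patients over time. If repeated days enter the correlation, these figures do not apply. They also say nothing about predictive ability.

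Finally, an encouragement-by-activity interaction term might seem the obvious remedy for the predictive half. An interaction tests a difference in slope, which is not a difference in predictive performance. The method described in Section 6.4 is anomaly detection with a modified Hotelling's T, not a regression.

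**Conclusion.** The point holds in limited form. Item 6 and its hypothesis concern a randomised difference, while the analysis text specifies only within-group repeats, with no interval or test for the difference. This is more than missing detail, because the method that is written invites the misreadings in steps 4 and 5. It touches one exploratory secondary outcome and leaves the primary EQ-5D analysis unaffected.

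The size is illustrative. It rests on assumed correlations, 25 v 25 in the Fitbit arms with no dropout, and one summary pair per patient; the power figures also assume one-sided 5%. On those terms only a large difference in correlation would be detected reliably. Predictive ability is not sized here, because the plan names neither a performance measure nor an expected number of events.

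**What to change.** In Section 6.4, Second phase, add that outcome 6 will be reported as:

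- the encouraged-minus-not-encouraged difference in wearable-phone correlation (arms 1 and 2), with a confidence interval from a bootstrap that resamples patients within each encouragement group; and
- the same difference in a named measure of predictive performance (all arms), with a patient-level bootstrap interval. The measure could be discrimination, or the contrast in anomaly rate between pre-event and other days, as in the schizophrenia cohort that the section cites.

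State whether the correlation is across patient averages or within patients over time. Resampling whole patients respects repeated readings in either case. Keep the within-group results as description and label the comparison exploratory.

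The cost is a few lines of analysis-plan wording and minor programming. No new data are needed, and the section already plans a bootstrap for Kappa. The price in interpretation is that the intervals will probably be wide.

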### 5.12 Second Phase

A feasibility and acceptability study will employ convenience sampling from 100 consecutive patients who meet inclusion criteria in a pilot randomized trial of:

- Arm 1: Fitbit + active app
- Arm 2: Fitbit + passive app
- Arm 3: Active app
- Arm 4: Passive app

There are two versions of the HOPE smartphone app—“active” and “passive.” The “active” smartphone app refers to the version of the smartphone app in which active symptom collection is occurring (e.g., patients are receiving surveys and receiving tailored symptom management advice) in addition to passive data collection (accelerometer, GPS, Incoming calls and texts, etc.) The “passive” smartphone app refers to the version of the smartphone app in which only passive data collection is occurring, and no surveys or active data collection are being sent to participants. In the passive app, participant interaction with the smartphone app consists of installing the app and keeping it running in the background of their phone; all data is collected in the background. The active and passive apps are built on the same underlying platform and the security protections for the active and passive smartphone apps are identical, detailed in Appendix L, HOPE App Data Privacy and Security.

All patients will be assigned to a separate, secondary randomization either to be encouraged to wear their smartphone on them at all times, or not to be encouraged to wear their smartphone at all times (refer to study schema for details.) We have no reason to believe that encouragement to wear a smartphone will impact patients’ health-related quality of life, performance status, and use of high-intensity health care/phone calls; thus, the secondary randomization will not impact the comparison of the 4 study arms for these outcomes.

With a total sample size of 100 patients (25 patients per arm), this study design will yield 70% power to detect a 6-point change in EQ-5D and 80% power to detect a 7-point change in patients’ health-related quality of life (measured with the EQ-5D; see section 6.0). Our analyses will also provide preliminary estimates of feasibility, acceptability, safety outcomes, scale scores, missing data, and participant and physician feedback.

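### The one-sided 5% rule for calling an intervention promising is tied to two tests per factor, an unadjusted t test and a covariate-adjusted regression, and the plan does not say which one decides

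*Combined protocol and SAP*

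**What the plan says.** The HOPE Trial, section 6.2, describes a 2x2 factorial design with 25 patients per arm and states the decision rule for EQ-5D change: "we will use a one-sided type I error rate of 5% to conclude that an intervention is promising for further study". It names no test.

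Section 6.4 (Second phase) opens its primary analysis by defining two contrasts of mean change: arms 1 and 2 against 3 and 4 for the Fitbit, and arms 1 and 3 against 2 and 4 for the app. It then says: "Mean score changes from baseline will be compared using t tests and multivariable linear regression". The regression takes the change score as outcome and adjusts for age, sex, cancer type, race, education, and literacy and numeracy.

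The text introduces the pairwise arm comparisons and the Fisher tests as additional. It gives the regression no such label, so it stands beside the t test inside the primary analysis. The other randomised factor is not mentioned for either method.

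**The concern.** A pass/fail rule needs one test statistic. Here each factor has two, which use different estimates and different error terms, so one can pass while the other fails. The plan does not say what is concluded then, and the choice would be open after both results are known. If that choice drifted towards whichever test was positive, the stated 5% would not hold.

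A second, smaller matter is how the factorial structure enters the test. A two-group t test cannot contain the other factor, and the description of the regression is silent on it. The one-factor contrast then relies on the other factor being equally represented on both sides. Randomisation in blocks provides this at entry, but loss of patients may not preserve it.

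**Working it through.** **Inputs from the documents.** One-sided 5% (6.2); "the standard deviation of the change in EQ-5D at 6 months compared to baseline is approximately 14 points" (6.2); 100 patients, 25 per arm, so 50 against 50 for each factor (6.2). Section 5.12 states that "this study design will yield 70% power to detect a 6-point change in EQ-5D and 80% power to detect a 7-point change".

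**Assumed inputs.** The share of variance in EQ-5D change explained by the covariates (R²) is taken as 0 to 0.3, and the number of covariate columns as 7, 10 or 12. The documents give neither.

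**1. The plan's power figures.** Main effect d, standard error 14 × √(2/50) = 2.80, power = Φ(d/2.80 − 1.645). When effects are not additive, d is the average of the simple effects; for example, the row 6, 3, 8 gives the app (6 + (8 − 3))/2 = 5.5.

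| d | Normal | t, 98 df | Stated in 6.2 |
|---|---|---|---|
| 6 | 69.1% | 68.6% | 70% (68% in the row 7, 3, 8) |
| 7 | 80.4% | 79.9% | 80% |
| 5.5 | 62.5% | 62.0% | 62% |
| 3 | 28.3% | 28.1% | 28% |
| 2.5 | 22.6% | 22.4% | 23% |
| 2 | 17.6% | 17.5% | 17% |

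The table is reproduced within 2 points by an unadjusted one-sided comparison of 50 with 50.

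**2. The two listed tests side by side.** Simulated balanced 2x2 trials of 100 patients, SD 14, comparing the pooled t test with a regression on the factor plus covariates, both one-sided 5%. There were 20,000 runs with no effect and 8,000 with a 6-point app effect per setting. Ranges are over 7, 10 and 12 columns.

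| R² | Either positive, no effect | Tests disagree, no effect | Tests disagree, 6 points | Power, t test | Power, regression |
|---|---|---|---|---|---|
| 0 | 5.8–6.5% | 2.2–2.8% | 7.8–10.7% | 67.6–68.2% | 62.9–64.9% |
| 0.1 | 6.5–6.8% | 3.2–3.8% | 11.1–13.9% | 67.5–69.2% | 66.7–69.6% |
| 0.2 | 7.1–7.4% | 4.3–4.6% | 14.7–15.7% | 67.5–69.9% | 71.9–74.9% |
| 0.3 | 7.2–7.8% | 4.9–5.3% | 17.2–18.4% | 68.3–69.3% | 76.9–79.0% |

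Each test alone stays near 5% (4.7 to 5.4%).

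**3. The other factor, balanced arms.** The t test and a two-factor linear model disagree in only about 0.1 to 0.6% of trials, and the two-factor model has 67 to 70% power at 6 points. Leaving a 6- or 7-point app effect in the error term raises the SD to √(196 + 3²) = 14.3 or √(196 + 3.5²) = 14.4. Wearable power at 3 points then falls from 28.1% to 27.3% or 27.0%. With no app effect and a 7-point Fitbit effect, the app t test rejects in 4.2% of trials, so the omission makes it slightly conservative.

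**4. The other factor, unequal losses.** Suppose 18, 23, 23 and 18 patients remain in arms 1 to 4, the Fitbit is worth 7 points and the app nothing. The Fitbit share is 18/41 among app patients and 23/41 among the rest. The app contrast is biased by 7 × (18 − 23)/41 = −0.85 points. With the reverse split the bias is +0.85. In simulation the t test's one-sided error moves to about 2.5% in the first case and 7.5% in the second. A model containing both factors removes the bias.

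**The case against.** The best reply is that the plan already points to the t test. It defines each effect as a difference in mean change between pooled arms, names the t test first, and rests its power table on an unadjusted comparison. That is a fair inference, and it means a reader should not conclude that the trial would have no answer at all. But no sentence makes the t test the decision rule, and nothing demotes the regression.

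Four further points on that side stand.

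- Nothing says that either positive test suffices, so the excess over 5% is conditional. It is also modest, in a pilot whose verdict is only that further study is worthwhile.
- A reader might infer that the missing factor causes the conflict between the two tests. It does not: step 3 shows that covariate adjustment accounts for nearly all of it. Nor does the text exclude the other factor from the regression; a list of baseline covariates is not a full model statement.
- A reader might also want the smartphone-encouragement randomisation in the model. Section 5.12 expects encouragement to have no effect on quality of life, and concludes that "the secondary randomization will not impact the comparison of the 4 study arms for these outcomes". The documents give no ground to override that.
- Section 6.5 excludes only patients with no post-baseline EQ-5D and carries the last value forward for the others, which limits how unequal the analysed arms can become. The split in step 4 is an illustration, not a forecast.

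**Conclusion.** The gap is real: one decision rule, two tests per factor, no ranking. At the 6-point effect for which section 5.12 quotes power, the tests would disagree in roughly 8 to 18% of trials. If either counted, the false-positive rate per intervention would be about 6 to 8%. Both ranges rest on the assumed R² of 0 to 0.3 and 7 to 12 covariate columns.

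The omitted factor is a secondary matter. It costs about 1 point of wearable power when arms are balanced, and biases the contrast by about 0.85 points in the unequal-loss example.

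A tempting stronger reading is that the trial as planned runs well above its stated error rate. The documents do not support that. The 5% is set per intervention, and even with one test each the chance of at least one false call across two interventions is 1 − 0.95² = 9.75%. That follows from testing two interventions, not from the gap described here.

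**What to change.** In section 6.4, name one deciding test per factor: a linear model for EQ-5D change containing both the Fitbit and the app factors, with each main effect tested one-sided at 5%. Its simulated power at 6 points is 67 to 70%, in line with section 6.2, so the sample size argument is unchanged. Compared with the t test it uses one more degree of freedom.

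Label the covariate-adjusted regression and the plain t tests as sensitivity or descriptive analyses. Drop sex from the covariate list, because it is constant in a trial that enrols only women, and state how the remaining covariates are coded.

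If the covariate-adjusted model is preferred as the deciding test, say so and restate its power at 6 points: about 63 to 66% if the covariates explain nothing (a loss of roughly 4 points), and about 77 to 79% if R² is 0.3.

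The encouragement factor need not be added. It would help to state that the 5% applies per intervention, so that the overall chance of a false call near 10% is a declared choice. The cost is a few lines of text and no new data.
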